9.4 STATISTICAL ANALYSES

9.4.1 Demographics and Baseline Characteristics

Demographics, including age, sex, weight, and height, as well as baseline characteristics such as prior cancer therapies, ECOG status, and medical history, will be described using basic summary statistics.

9.4.2 Efficacy Analyses

The efficacy analyses will include all patients in the efficacy analysis populations as defined in [Table 10](#).

The primary analysis will be triggered by at least 20 efficacy-evaluable, ruxolitinib-naïve patients, or at least 20 efficacy-evaluable, ruxolitinib-resistant or intolerant patients. Primary, secondary, and exploratory endpoints (see [Table 3](#)) will be analyzed using listings and summary statistics as appropriate. No formal statistical model and no formal hypothesis testing are planned in this study.

Patients with missing assessments (hematology and/or splenic imaging) that prevent evaluation of efficacy endpoints will be considered NR. To be considered as having Hct control (absence of phlebotomy eligibility) between Week 8 and Week 32, the patient cannot miss more than one scheduled Hct assessment during this period.

A detailed description of the statistical methods that will be used for the efficacy analyses will be provided in the SAP.

Interim analyses may be performed to evaluate preliminary results and to confirm continuous positive benefit/risk profile (see Section 9.5).

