9.2 SAMPLE SIZE DETERMINATION

9.2.1 Sample Size in Ruxolitinib-Naïve Patients

Approximately 20 efficacy-evaluable patients without prior ruxolitinib exposure will be enrolled.

For 12 patients who are ruxolitinib-naïve with splenomegaly, observing a composite response rate of 50% (6/12) would provide a posterior probability of 85% that the true rate is greater than a 35% response rate. A 35% composite response rate is the minimum response rate to be considered of interest ([Vannuchi et al. 2015](#)).

Assuming a true composite endpoint rate of 60%, there is an 84% probability of observing at least 6 responders out of 12 patients.

In 20 ruxolitinib-naïve patients, observing a Hct control rate of 70% (14/20) would provide a posterior probability of 80% that the true rate is greater than 60%. Assuming a true Hct control rate of 75%, there is a 79% probability of observing at least 14 responders out of 20 patients.

Based on the results from *the trials RESPONSE and RESPONSE-2* in patients *with and without splenomegaly*, a 60% Hct control rate is the minimum response rate to be considered of interest. For 8 patients who are ruxolitinib-naïve without splenomegaly, observing a Hct control rate of 75% (6/8) would provide a posterior probability of 79% that the true rate is greater than 60%. Assuming a true Hct control rate of 75%, there is a 68% probability of observing at least 6 responders out of 8 patients.

For all 20 ruxolitinib-naïve patients, observing CHR of 45% (9/20) would provide a posterior probability of 81% that the true rate is greater than 35%. Assuming a true rate of 50%, there is 75% probability of observing at least 9/20 responders. Up to 20 additional patients may be enrolled to confirm safety, efficacy, and/or PK.

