9.3 POPULATIONS FOR ANALYSES

For purposes of analysis, the following *two main populations (and combined populations)* will be described as defined in [Table 10](#):

- *Ruxolitinib-naïve patients*
- *Ruxolitinib-resistant or intolerant patients*

Additional populations may be defined in the Statistical Analysis Plan (SAP).

Table 10 Analysis Populations for Ruxolitinib-Naïve and Ruxolitinib-Resistant or Intolerant Patients

Description Analyses Per Population and Combined Populations	
Efficacy	Primary efficacy population consists of patients who have completed at least 32 weeks of treatment or withdrew prior to Week 32 due to NR or progressive disease. There will also be an early-look efficacy population consisting of patients who have completed at least 3 and/or 5 cycles.
Safety	All patients who received at least one dose of the study treatment, whether prematurely withdrawn from the study or not, will be included in the safety analysis.
PK	All patients who have received at least one dose of study treatment and who have data from at least one post-dose sample will be included in the PK analysis population. Patients will be excluded from the PK analysis population if they significantly violate the inclusion or exclusion criteria, deviate significantly from the protocol, or if data are unavailable or incomplete which may influence the PK analysis. Excluded cases will be documented together with the reason for exclusion. All decisions on exclusions from the analysis will be made prior to database closure.
Pharmacodynamic	All patients who had at least one pre-dose and one post-dose pharmacodynamic assessment will be included and analyzed.

ITT=intent-to-treat; NR=no response; PK=pharmacokinetic.

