3. FILTERS, POPULATIONS AND SUBGROUPS

Filter Category	Label of population or subgroup	Filter	Description
Main Populations	Safety-Evaluable Patients	SE	All patients who received at least one dose of the study treatment, whether prematurely withdrawn from the study or not, will be included in the safety analysis.
	Intent-to-Treat Patients	IT	All enrolled patients, regardless of previous ruxolitinib treatment
	Primary Efficacy Patients	PE	Ruxolitinib-naive patients both with splenomegaly by imaging or without splenomegaly who have Completed at least 32 weeks of treatment or withdrew prior to Week 32 due to NR or progressive disease.
	Early-Look Efficacy Patients	ELE	Patients who have completed at least 3 and/or 5 cycles

	PK Patients	PK	All patients who have received at least one dose of study treatment and who have data from at least one post-dose sample will be included in the PK analysis population. Patients will be excluded from the PK analysis population if they significantly violate the inclusion or exclusion criteria, deviate significantly from the protocol, or if data are unavailable or incomplete which may influence the PK analysis. Excluded cases will be documented together with the reason for exclusion. All decisions on exclusions from the analysis will be made prior to database closure.
	Pharmacodynamic Patients	PD	All patients who had at least one pre-dose and one post-dose pharmacodynamic assessment will be included and analyzed.
	Prior Rux exposed patients	RUX	
	Patients with splenomegally	SPLNML	All patients with splenomegaly
	Patients without splenomegally	WOSPLML	
	All Rux naïve	RUXNAIVE	
Sub-setting of data by patient characteristics – key subgroups only	Patients aged >= 65	AGEGE65	Patients aged 65 or more

Additional filters are used to subset data based on assessments, e.g. serious adverse events or assessments during treatment.

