5.7 Efficacy Analysis

5.7.1 Primary endpoint Response rate: Hct Criteria

The primary endpoint will be evaluated based on *hematocrit control* on the following populations

- All Patients without prior ruxolitinib exposure without Splenomegaly
 - Response is defined HCT control i.e. ≤ 1 instance of phlebotomy eligibility between first dose and Week 8; and ineligibility for phlebotomy between week 8 and Week 32 based on CRF;
Definition of eligibility for phlebotomy: a Hct of $\geq 45\%$ that was $\geq 3\%$ higher than baNPseline level or a Hct of $> 48\%$.
- Patients without prior exposure to ruxolitinib with Splenomegally
 - Using composite:
 - HCT control
 - $\geq 35\%$ reduction in spleen volume (primary at Week 32) from baseline
- All patients without prior exposure to Ruxolinitib with or without splenomegally
 - HCT control
 - Using HCT control without phlebotomy Notes:

A summary table for the response rates will be provided (RSPT01). Only descriptive statistics are used. No formal testing is done in the study.

RSPT01

Overview of response rate
Primary Efficacy Evaluable Population {, subgroup}
Protocol: {base protocol}

Overall At Week 32	Ruxolitinib Naïve (N=xx)			Ruxolitinib Exposed (N=xx)			All Patients (N=xx)
	With Splenomegaly (N=xx)	Without Splenomegaly (N=xx)	All Patients (N=xx)	With Splenomegaly (N=xx)	Without Splenomegaly (N=xx)	All Patients (N=xx)	
HCT Control	xx (xx.x%)	xx (xx.x%)	xx (xx.x%)	xx (xx.x%)	xx (xx.x%)	xx (xx.x%)	xx (xx.x%)
95% CI	(x.xx, x.xx)	(x.xx, x.xx)	(x.xx, x.xx)	(x.xx, x.xx)	(x.xx, x.xx)	(x.xx, x.xx)	(x.xx, x.xx)
Not Evaluable (NE)	xx (xx.x%)	xx (xx.x%)	xx (xx.x%)	xx (xx.x%)	xx (xx.x%)	xx (xx.x%)	xx (xx.x%)
Missing	xx (xx.x%)	xx (xx.x%)	xx (xx.x%)	xx (xx.x%)	xx (xx.x%)	xx (xx.x%)	xx (xx.x%)
Composite Response %	NA	NA	xx (xx.x%)	NA	NA	xx (xx.x%)	xx (xx.x%)
95% CI	NA	NA	(x.xx, x.xx)	NA	NA	(x.xx, x.xx)	(x.xx, x.xx)
Not Evaluable (NE)	NA	NA	xx (xx.x%)	NA	NA	xx (xx.x%)	xx (xx.x%)
Missing	NA	NA	xx (xx.x%)	NA	NA	xx (xx.x%)	xx (xx.x%)

Patients were classified as "Not Evaluable" if all post-baseline response assessments were reported as not evaluable, or SD assessment occurring within xxx weeks from baseline/study entry.

Patients were classified as "Missing" if no post-baseline response assessments were available.

Notes

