5.7.2.2 Complete Hematologic response (CHR)

Similarly to be evaluated on the 3 Rux naïve populations: without splenomegaly, with splenomegaly; and with and without splenomegaly.

Complete hematologic response (CHR) requires all of the following:

- Hct control (protocol-specified ineligibility for phlebotomy between Weeks 8–32 and ≤ 1 instance of phlebotomy eligibility between first dose and Week 8);
- WBC count ≤ 10 × 10⁹/L at Week 32 assessment; AND
- PLT count ≤ 400 × 10⁹/L at Week 32 Assessment

Response rate per Complete Hematologic Response
Intent-to-Treat Patients
Protocol: {base protocol}

	Ruxolitin b Naïve (N=xx)				Ruxolitin b Exposed (N=xx)				All Patients (N=xx)	
	With Splenomegaly (N=xx)		Without Splenomegaly (N=xx)		With Splenomegaly (N=xx)		Without Splenomegaly (N=xx)			
	Cycle 3 Day 28 (N=xx)	Cycle X Day XX (N=xx)	Cycle 3 Day 28 (N=xx)	Cycle X Day XX (N=xx)	Cycle 3 Day 28 (N=xx)	Cycle X Day XX (N=xx)	Cycle 3 Day 28 (N=xx)	Cycle X Day XX (N=xx)	Cycle 3 Day 28 (N=xx)	Cycle X Day XX (N=xx)
CHR	xx (xx.x%)	xx (xx.x%)	xx (xx.x%)	xx (xx.x%)	xx (xx.x%)	xx (xx.x%)	xx (xx.x%)	xx (xx.x%)	xx (xx.x%)	xx (xx.x%)
95% CI	(x.xx, x.xx)	(x.xx, x.xx)	(x.xx, x.xx)	(x.xx, x.xx)	(x.xx, x.xx)	(x.xx, x.xx)	(x.xx, x.xx)	(x.xx, x.xx)	(x.xx, x.xx)	(x.xx, x.xx)
Complete Response (CR)	xx (xx.x%)	xx (xx.x%)	xx (xx.x%)	xx (xx.x%)	xx (xx.x%)	xx (xx.x%)	xx (xx.x%)	xx (xx.x%)	xx (xx.x%)	xx (xx.x%)

Note: Time points as per the protocol assessment schedule.

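### The SAP's CHR table uses all enrolled patients and has no all-naive or all-exposed column, so the benchmarked CHR rate (9/20 against 35%) is not specified on the population it was sized on

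*Protocol*

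**What the plan says.** **Protocol.** Section 9.4.2 states: "The efficacy analyses will include all patients in the efficacy analysis populations". The same section lists primary, secondary and exploratory endpoints as the ones to be analysed. Table 10 in 9.3 defines two efficacy populations and applies them to both cohorts and to the cohorts combined. The main one is described thus: "Primary efficacy population consists of patients who have completed at least 32 weeks of treatment or withdrew prior to Week 32 due to NR", with progression before that time treated the same way. The other is an early-look set, made up of patients with three and/or five cycles behind them.

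Section 9.2.1 plans for about 20 efficacy-evaluable naive patients. For all 20 it states that "observing CHR of 45% (9/20) would provide a posterior probability of 81% that the true rate is greater than 35" per cent. CHR is also a secondary endpoint for the ruxolitinib-resistant or intolerant cohort (protocol Table 3 and synopsis).

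**SAP.** Section 5.7.2.2 says of CHR: "Similarly to be evaluated on the 3 Rux naïve populations: without splenomegaly, with splenomegaly; and with and without splenomegaly". The shell beneath that sentence is headed "Intent-to-Treat Patients", which SAP section 3 defines as "All enrolled patients, regardless of previous ruxolitinib treatment". Its columns are naive with and without splenomegaly, exposed with and without splenomegaly, and one column for all patients. The duration shell in 5.7.2.3 has the same label and columns. The by-visit response shell in 5.7.1 is also labelled Intent-to-Treat. Only the Week 32 table RSPT01 uses the Primary Efficacy population.

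**The concern.** CHR in all naive patients is the only secondary endpoint to which the protocol's sample size section attaches a numerical benchmark. A reader will look for one number to set beside 45% and 35%. The CHR shell differs from that number in two ways:

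- **Denominator.** It counts everyone enrolled, whereas the sizing counts evaluable patients.
- **Grouping.** It splits the naive cohort by spleen status and then pools it with a pretreated cohort that has its own planning assumptions. The whole naive cohort has no rate or confidence interval of its own.

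For the exposed cohort, neither the CHR text nor the CHR shell provides a whole-cohort result. SAP 5.7.2.5 covers only Hct control and composite response there.

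The Early-Look population is a related gap. Both documents define it, but no efficacy shell supplied uses it, and the Cycle 3 and Cycle 5 results appear on all enrolled patients.

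**Working it through.** **1. Reproduce the plan's figures (protocol 9.2.1).**

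P(X ≥ 9 | n = 20, p = 0.50) = 0.748, against a stated 75%.

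The posterior for a rate p after x responders in n, with a Beta(a, b) prior, is Beta(a + x, b + n − x). The protocol does not state its prior. P(p > 0.35 | 9/20) is:

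- Beta(1, 1): 0.838
- Beta(0.5, 0.5): 0.827
- Beta(0.35, 0.65): 0.809
- Beta(0.35, 0.55): 0.813

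The last prior reproduces all five posterior figures in 9.2 to within one percentage point. The planning figures are therefore sound. The problem is where the result will be reported.

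**2. Compare the table columns.**

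| Column | Default header (SAP 5.1) | RSPT01 and by-visit shell (5.7.1) | CHR and duration shells (5.7.2.2, 5.7.2.3) |
|---|---|---|---|
| Naive, with / without splenomegaly | yes | yes | yes |
| All naive | yes | yes | **no** |
| Exposed, with / without splenomegaly | yes | yes | yes |
| All exposed | yes | yes | **no** |
| Both cohorts pooled | yes | yes | yes |

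The all-naive count can be recovered by adding the two strata, but its interval cannot be read off. Take the planned 12/8 split and an assumed 5/12 and 4/8. The strata give exact 95% intervals of 15.2–72.3% and 15.7–84.3%. The sum, 9/20, gives 23.1–68.5%, and that line is not in the shell.

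**3. Why the denominators can differ.** Protocol 7.1 and 7.2 allow replacement of patients who withdraw before Week 32 for reasons other than no response or progression. Such patients leave the evaluable set but remain enrolled.

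**4. Size, for illustration.** Hold the responders at 9 and add enrolled patients who count as non-responders. The number added is an assumption, because the documents give none.

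| Extra enrolled | CHR | Exact 95% CI | P(p > 35%), Beta(1, 1) | P(p > 35%), Beta(0.35, 0.55) |
|---|---|---|---|---|
| 0 | 9/20 = 45.0% | 23.1–68.5% | 84% | 81% |
| 2 | 9/22 = 40.9% | 20.7–63.6% | 74% | 71% |
| 4 | 9/24 = 37.5% | 18.8–59.4% | 63% | 59% |
| 6 | 9/26 = 34.6% | 17.2–55.7% | 52% | 47% |

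The direction is the same under both priors. With no extra patients the two denominators coincide.

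**The case against.** Several counter-arguments have force.

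**The analysis may still be produced.** A reader might infer from the shell that the all-naive CHR rate will never appear. The documents do not support that. The SAP text asks for naive patients with and without splenomegaly, the default header in 5.1 has both whole-cohort columns, and the complete output list is a separate document that is not supplied. What can be shown is a conflict between text and shell.

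**Hct control can be read on the same set.** A reader might also infer that CHR cannot be compared with its Hct component in the same patients. That fails too. The Intent-to-Treat by-visit shell continues to a generic later visit under the protocol's assessment schedule, which includes Week 32.

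**The shells are templates.** Some still carry columns from other trials, so a missing column is weak evidence of intent. This tempers the grouping point. It does not explain the population label, which recurs across three efficacy shells while RSPT01 carries a different one.

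**The SAP may add populations.** Protocol 9.3 allows this, and an all-enrolled CHR table is a legitimate addition. The permission does not say that an added set replaces the efficacy population named in 9.4.2.

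**The printed denominator is itself uncertain.** SAP 4.4 bases percentages on patients with non-missing information, whereas protocol 9.4.2 counts missing assessments as no response. The CHR shell has no Missing or Not Evaluable rows. The 9/22 to 9/26 figures follow the protocol rule and are not a forecast of what the SAP would print.

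**The consequence is limited.** All analyses are descriptive, and the expansion criterion in 9.2.2 is Hct control. This stands.

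**Conclusion.** The point holds in a bounded form. The SAP's CHR shell departs from protocol 9.4.2 in its population, and from the SAP's own text and default header in its columns. The all-naive, efficacy-evaluable CHR rate, the only secondary result with a benchmark, is therefore not specified on the population it was sized on. The gap is firmer for the exposed cohort, where neither the CHR text nor its shell gives a whole-cohort rate. The duration shell shares both faults. The by-visit shell shares only the population label.

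The effect ranges from none to a fall from 45% to 34.6%, with the posterior probability dropping from about 81–84% to about 47–52%. That range rests on three assumptions: 0 to 6 extra enrolled patients, all counted as non-responders, and a prior the protocol does not state. No error rate or go/no-go rule is affected. The change is worth making before results are seen, because it settles which CHR rate is compared with 35%.

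**What to change.** 1. Extend the SAP Primary Efficacy definition, now limited to naive patients, to the resistant/intolerant cohort, as in protocol Table 10. This comes first, because otherwise exposed columns on that set would be empty.
2. Report CHR and durable response on that population, with All Ruxolitinib Naive and All Ruxolitinib Exposed columns and 95% confidence intervals. Keep Intent-to-Treat as a second, labelled table.
3. State that the all-naive efficacy-evaluable CHR rate is the one compared with 35%.
4. Show Cycle 3 and Cycle 5 response on the Early-Look set as well as on Intent-to-Treat.

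The cost is one revised definition, edits to a few shells and some extra summary tables. The downside is two rates per endpoint, one possibly lower.

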9.4.3 Safety Analyses

All safety analyses will be based on the safety analysis populations.

Safety will be determined by AE, laboratory tests, vital signs, and electrocardiograms. Descriptive statistics will be used to summarize all safety data.

Exposure to study medication will be summarized by total duration of study medication, number of cycles started and cumulative dose using descriptive statistics.

All clinical laboratory data will be stored on the database in the units in which they were reported. Patient's listings and summary statistics at each assessment time will be presented using the International System of Units (SI units; *Système International d'Unités*). Laboratory data not reported in SI units will be converted to SI units before processing. See [Appendix 9](#) for details on standard reference ranges and data transformation and the definition of laboratory abnormalities.

Table 11 Safety Statistical Analysis Methods

Endpoint	Statistical Analysis Methods
Adverse events	
The original terms recorded on the eCRF by the Investigator for AE will be coded by the Sponsor using the latest MedDRA version available at time of CCOD. AE severity will be graded according to NCI CTCAE v4.0. AE will be summarized by mapped term and appropriate thesaurus level. Individual patient listings will be produced.
 
Safety analyses will include, but not be limited to, incidence rates for adverse events including mortality, adverse event severity, seriousness, and adverse events leading to discontinuation. The incidence of treatment discontinuation for reasons other than disease progression will be summarized.

Clinical laboratory tests	
Laboratory test values will be presented in SI units by individual listings with flagging of values outside the normal ranges. In addition, tabular summaries will be produced, as appropriate.
 
Shifts in NCI CTCAE v4.0 grades from baseline to the worst grade observed during treatment will be presented for selected laboratory parameters. Individual patient listings will be produced. See Appendix 9 for details on standard reference ranges, data transformation, and the definition of laboratory abnormalities.

Vital signs	
Vital signs data will be presented by individual listings with flagging of values outside the normal ranges and flagging of marked abnormalities. In addition, tabular summaries will be used, as appropriate. Individual patient listings will be produced.

ECG data analysis	
ECG data will be presented by individual listings. In addition, tabular summaries will be used, as appropriate. Incidence of clinically significant ECG abnormalities will be reported in patient listings and change from baseline summarized in tables.

Concomitant medications	
The original terms recorded on the patient's eCRF by the Investigator for concomitant medications will be standardized by the Sponsor by assigning preferred terms using MedDRA version available at time of CCOD.
 
Concomitant medications will be presented in summary tables and listings.

AE=adverse event; CCOD=clinical cut-off date; eCRF=electronic Case Report Form; MedDRA=Medical Dictionary for Regulatory Activities; NCI CTCAE=National Cancer Institute Common Terminology Criteria for Adverse Events; SI=International System of Units.

9.4.4 Pharmacokinetic Analyses

The PK evaluations for this study are as follows:

- Maximum concentration (C_{max})
- Trough concentration (C_{trough})
- Time of maximum concentration (t_{max})
- Clearance (CL) or apparent clearance (CL/F) for drugs given extra-vascularly

- Volume or apparent volume of distribution ($V_{d_{ss}}/F$)
- Area under the curve (AUC)
- Half-life ($t_{1/2}$)
- Potentially other parameters derived

All PK parameters will be presented by listings and descriptive summary statistics as appropriate.

Individual and mean plasma idasanutlin concentration versus time data will be tabulated and plotted by dose level. The plasma PK of idasanutlin will be summarized by estimating total exposure (AUC), maximum concentration, total clearance, volume of distribution at steady-state, and terminal half-life. Estimates for these parameters will be tabulated and summarized (mean, standard deviation, coefficient of variation, median, minimum, and maximum). Inter-patient variability and drug accumulation will be evaluated.

Both non-compartmental analysis (NCA) and population PK (popPK) as well as potential association with effects (efficacy, AEs, and biomarkers) will also be applied or explored with results either reported in the CSR or a separate report.

Additional PK analyses will be conducted as appropriate.

9.4.5 Pharmacodynamic Analyses

All pharmacodynamic parameters will be presented by listings and descriptive summary statistics as appropriate.

9.4.6 Clinical Outcome Assessment Analyses

The MPN-SAF TSS, EORTC QLQ-C30, and PGIC will be used to measure symptoms of PV, physical functioning, global health status/*HRQoL*, and change in condition. Data will be used to derive summary scores at each timepoint. Appropriate summary statistics (frequency, mean, standard deviation, median, and range) of absolute scores will be calculated for the PGIC and all scales of the MPN-SAF TSS and EORTC QLQ-C30, at each assessment point, for all patients. Individual trajectories (e.g., spaghetti plots) and line graphs will be used to chart patient- and mean-level change over the course of the study. Mean change from baseline to each follow-up assessment point will be calculated for the scales of the MPN-SAF TSS and EORTC QLQ-C30. Frequencies will be used to show the distribution of responses to the PGIC at each assessment point. Results will be further stratified by splenomegaly at baseline. COA completion and compliance rates will be summarized at each assessment point with reasons for missing data.

